- (f) is otherwise considered medically significant by the investigator.

The study will monitor the occurrence of any serious adverse event which arises whilst the participant is taking part in the ADEPT trial.

Participants, researchers and clinical staff should notify any adverse event which they believe may have occurred as a result of the trial intervention or the research process. On notification of such an adverse event which may be related to the research process or intervention, a researcher or member of site staff should complete an adverse event report form within 5 working days, paying specific attention to information regarding the nature and timescale of events i.e. when the event started,

were there any specific changes to medication or behaviour preceding the event. Further information should be requested from the participant, clinical team or GP as necessary. A completed form should be securely sent to the Chief Investigator for review and assessment of relatedness and expectedness as follows:

- 1. Confirmation of seriousness (whether the adverse event is an AE or SAE)
- 2. Causality i.e. relatedness of the event to the study intervention, according the following definitions:

Unrelated – where an event is not considered to be related to the study intervention Possibly – although a relationship to the study intervention cannot be completely ruled out, the nature of the event, the underlying disease, concomitant medication or temporal relationship make other explanations possible

Probably – the temporal relationship and absence of a more likely explanation suggest the event could be related to the study intervention

Definitely – Known effects of the study intervention, or based on challenge testing, suggest that study intervention is the most likely cause.

3. Expectedness of the event. Is the event an anticipated event even if the research had not been taking place?

Serious Adverse Event reporting

All SAEs will be reported to the Chief Investigator within 24 hours of awareness of the SAE. All SAEs that occur in relation to the intervention must be recorded, together with data including date of onset and resolution, outcome, severity and causality for the intervention.

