All SAEs of a related and unexpected nature will require onward reporting to the main REC, and this will be facilitated by the Chief Investigator, in accordance with any procedures of the Sponsor. Related and unexpected SAEs will be immediately reported to the Sponsor. In addition all investigators will be notified, and the TSC will be notified in accordance with Sponsor procedures and timeframe. SAEs which after review are not thought to be treatment related will be brought to the TSC's attention at their next scheduled meeting. The numbers and details of AEs and SAEs will be reported to the Trial Management Group and Trial Steering Committee regularly.

22. Auditing

The Chief Investigator will be responsible for the day to day monitoring and management of the study. The Principal Investigators at each site will monitor the management of the study within that site. The Sponsor will monitor and conduct random audits on a selection of studies in its clinical research portfolio. Monitoring and audit will be conducted in accordance with the DH research Governance Framework for Health and Social Care and in accordance with the Sponsor's policies and procedures.

Nested Qualitative Study

The acceptability of the intervention to adults with Autism and Therapists

In-depth interviews will be conducted with participants (from both arms of the trial) 10 weeks after randomisation (after the primary outcome has been collected). For face-to-face qualitative interviews participants will be asked to complete a written consent form. For telephone qualitative interviews the researcher will verbally explain consent to the participant before the interview starts and, if the participant confirms their agreement to the interview, the verbal consent agreement will be repeated and audio recorded.

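### Events arising from the research process must be notified, but causality is graded against the study intervention only, so a serious unexpected event caused solely by a study procedure does not trigger REC, immediate sponsor or investigator reporting

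*Protocol*

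**What the plan says.** All of this is in Protocol section 21 (Safety assessments and monitoring) unless noted.

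- **Notification.** Participants, researchers and clinical staff are to "notify any adverse event which they believe may have occurred as a result of the trial intervention or the research process". The report-form sentence repeats this scope: "On notification of such an adverse event which may be related to the research process or intervention", a form is due within 5 working days.
- **Causality.** The Chief Investigator then assesses "Causality i.e. relatedness of the event to the study intervention, according the following definitions". There are four grades (Unrelated, Possibly, Probably, Definitely). The lowest applies "where an event is not considered to be related to the study intervention", and the other three also refer to the study intervention.
- **Expectedness.** The test is "Is the event an anticipated event even if the research had not been taking place", so it looks at the research as a whole.
- **SAE recording.** "All SAEs that occur in relation to the intervention must be recorded", with causality again recorded for the intervention. Separately, every SAE goes to the Chief Investigator within 24 hours.
- **Onward reporting.** An SAE that is both related and unexpected must go to the main REC, goes immediately to the sponsor, and is notified to all investigators and the TSC. By contrast, "SAEs which after review are not thought to be treatment related will be brought to the TSC's attention at their next scheduled meeting".
- **Committees section.** The Trial Management Group's duties include reporting AEs and SAEs to the TSC, DMEC, sponsors and funders, with no condition on relatedness.

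**The concern.** Two scopes are applied to the same event. The wide one (intervention or research process) decides what is notified and put on a form. The narrow one (intervention only) decides how the event is classified, and the classification decides who is told and how soon. No grade or field says that a study procedure caused an event.

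The procedures in question are substantial. Participants are adults with current depression (PHQ-9 of 10 or more). Both arms repeat the PHQ-9, with its suicide item, and the Hamilton interview at baseline and at 10, 16 and 24 weeks, and complete the CIS-R at baseline. Some have a qualitative interview of 45 to 60 minutes, during which the protocol itself foresees possible distress. If one of these procedures caused serious harm, the REC and sponsor would need to know promptly, as would the designers of the full RCT.

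**Working it through.** No figure in the plan needs reproducing. The check is to follow one case through section 21: a serious, unexpected event caused solely by a research assessment or interview.

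1. **Is it notifiable?** Yes. It is believed to result from the research process, which is named.
2. **Is a form completed and the Chief Investigator told?** Yes. The form covers the research process, and all SAEs reach the Chief Investigator within 24 hours.
3. **What is the causality grade?** The question is relatedness to the study intervention. By construction of the case there is none, so the definition of *Unrelated* is met. No other grade fits.
4. **Is it expected?** The test asks whether the event would be anticipated without the research. An event caused by a research procedure would not be, so it counts as unexpected. Item 3 therefore takes the research process into account, while item 2, just above it, does not.
5. **Does it meet the related-and-unexpected trigger?** No. It is unexpected but not graded related. The REC report, the immediate sponsor report and the notice to investigators are not required.
6. **Where does it go?** To the TSC at its next scheduled meeting, as an SAE not thought to be treatment related.

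**By arm.**
- TAU participants do not receive GSH, so for them the wording gives no basis for any grade above *Unrelated*. Treating TAU as a comparator intervention does not help, because the event in this case is not caused by TAU either.
- In GSH the result is strict only when the procedure is the sole cause. Where the cause is unclear, *Possibly* is available, because it covers events for which a link to the intervention cannot be fully excluded. Overlap is likely in GSH because the PHQ-9 is also given at the start of each session.

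**Exposure** (sections 16 and 30; Sampling in the Nested Qualitative Study), assuming full recruitment and retention:
- Assessments: 70 participants × 4 time points = 280.
- TAU share: 35/70 = 50%, which is 35 × 4 = 140 assessments.
- Qualitative interviews with participants: up to 16 + 8 = 24, of which 8 are in TAU.

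These count opportunities, not events. The protocol gives no rate of serious procedure-caused events, so no expected number can be calculated.

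**The case against.** The strongest reply is that the two rules can both be obeyed. A wide notification net followed by a narrower causality scale is an omitted category, not a logical contradiction. That stands as a description, but it does not change the route the event takes.

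A second reply is that *related*, in the REC and sponsor sentences, is not expressly tied to treatment, that REC reporting also follows sponsor procedures that are not shown, and that a Chief Investigator could read the word broadly. This is possible. But section 21 defines relatedness only once, against the study intervention, and the TSC sentence speaks of treatment-related events, which supports the narrow reading.

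A third reply is that other routes exist, and this stands in full. A reader might infer that such events go unrecorded, or that the trial would show zero procedural harm. The protocol does not support that: the report form captures their nature and timing, adverse events are collected at 10, 16 and 24 weeks, and the qualitative interviews in both arms cover experience of the trial. Only the causality grade fails to label the cause. Nor can one infer that the sponsor would never hear, because the Committees section provides for general AE and SAE reporting to sponsors without regard to relatedness. Nor is every procedure-caused event in GSH bound to be graded *Unrelated*, given the *Possibly* grade.

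**Conclusion.** The point holds as a wording gap with a definite effect on reporting. Read as written, section 21 sends a serious unexpected event caused solely by a research procedure past the REC report, the immediate sponsor report and investigator notification. The immediacy lost is the sponsor's. The REC report is required for related and unexpected SAEs but carries no stated time limit, so a missed REC deadline cannot be claimed.

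The gap covers a subset of events: those with a purely procedural cause, in either arm. It touches no feasibility estimate. Its frequency is unknown and may be very low. The conclusion assumes that *related* keeps the one meaning section 21 gives it and that no sponsor procedure outside the protocol overrides it. Because it concerns required safety reporting and is cheap to correct, it should be corrected.

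**What to change.** Reconcile the parts of section 21 so that one scope runs from notification to onward reporting:

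- In the causality item, replace *study intervention* with *study intervention or research procedures* in the stem and in all four definitions.
- Add a field to the adverse event report form stating which of the two is implicated.
- Extend the SAE recording sentence, and its reference to causality for the intervention, in the same way. Otherwise an intervention-only rule would remain beside the corrected scale.
- In the sentence on TSC reporting, replace *treatment related* with *related to the intervention or research procedures*.

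The AE definition that opens section 21 is also worded around treatment and therapy, and should be read against the same scope when the edits are made.

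The cost is a few words, one form field and slightly more form work. There may be some additional reports to the REC and sponsor; their number cannot be estimated from the protocol.

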- Participants where intellectual disability is known or suspected will be excluded as the selfhelp materials will not be modified in line with their needs
- o Risk of suicide participants who endorse a score of 3 on Item 9 of the PHQ-9 will be followedup by the lead clinical researcher on each site to assess suicidal risk. Where clinic assessment or research follow-up is indicative that there is a current risk of suicidality such that a lowintensity intervention would not be clinically appropriate, this will be communicated to the relevant health care professional (e.g. referring ASD clinic and/or GP) and the participant will

be excluded from the study. Risk may increase during the study as evidenced by session by session administration of the PHQ-9 for those in the GSH group. If increased risk is identified following review of the case in clinical supervision, the therapist guide and clinical supervisor will discuss whether referral to statutory health services and discontinuation in the study is indicated.

- Participants with a history of psychosis, current alcohol/substance dependence or untreated epilepsy will be excluded
- Participants who report that they have attended > 6 sessions of individual psychological treatment within a CBT framework over the past 6 months will be excluded from the study
- o Participants who are non-English speaking as the intervention takes the form of written materials and therapist discussion which requires a sufficient level of English to access.

12. Recruitment

Patient identification

Participants will be identified by (i) clinicians in the Bristol Adult Autism Service (BASS) within AWP, (ii) 'Everybody Included' within AWP, (iii) clinicians in the Adult Autism Clinic in NTW and (iv) the Autism Spectrum Cohort-UK at Newcastle University.

There are different versions of patient identification according to local clinical and recruitment procedures and these are outlined below.

i) Adult Autism Clinic in AWP

The PHQ-9 is administered as part of pre-clinic screening. Clinicians will identify individuals attending the clinic who meet the eligibility criteria i.e. PHQ-9 score ≥ 10 for the study.

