Information capable of identifying individuals will be held on the database with passwords restricted to authorised study staff only.

19. Statistical Analysis

For this feasibility study, we will calculate: (1) the proportion of adults with ASD consenting to the study; (2) the proportion completing the baseline assessment and entering the randomised phase; (3) for those in the intervention group, the number of guided self-help sessions attended and the proportion completing 5 or more sessions; (4) the proportion completing follow-up assessments at 10 and 16 weeks post-randomisation. We will also compare the continuous scores on the depression outcome measure between groups. The standard deviation of the outcome will inform the sample size calculation for the large-scale RCT.

Methods: Monitoring

20. Data Monitoring

A Data Monitoring and Ethics Committee will be convened with an independent Chair, and will monitor accumulating trial data during the course of the study and make recommendations to the Trial Steering Committee as to whether there are any ethical or safety issues that may necessitate a modification to the trial protocol.

21. Safety assessments and monitoring

Adverse Events (AE)

The recommendations for defining and reporting adverse events and harm from psychological therapies as outlined by Parry, Crawford and Duggan (2016) will be used in the Adept Study. An Adverse Event (AE) refers to:

- (a) A significant episode during or shortly after treatment (e.g. suicide, suicide attempts, mental health related hospital admissions) which if related to or directly caused by treatment amount to harm or severe harm
- (b) A sustained and clinically significant deterioration i.e. a worsened mental state after therapy is complete, which can include the emergence of new symptoms. For the purposes of the present study this would be reflected in a categorical negative change in scores on 1 or more of the depression measures used in the study across 2 follow-up points
- (c) Report of a negative experience of the psychological intervention and perceived harm on the part of the participant when interviewed for the nested qualitative study.

Serious Adverse Events (SAEs)

A serious adverse event (SAE) is defined as an untoward occurrence that:

- (a) results in death;
- (b) is life-threatening;
- (c) requires hospitalisation or prolongation of existing hospitalisation;
- (d) results in persistent or significant disability or incapacity;

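### The expectedness test in Protocol Section 21 lets a treatment-related SAE be classed as expected because depression can cause it, and a related but expected SAE then has no timed route beyond the Chief Investigator

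*Protocol*

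**What the plan says.** Protocol Section 21 has the Chief Investigator make three assessments of a notified event: seriousness, causality and expectedness.

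- **Causality** is a separate item: "Causality i.e. relatedness of the event to the study intervention, according the following definitions". The four grades are unrelated, possibly, probably and definitely.
- **Expectedness** is settled by one question: "Is the event an anticipated event even if the research had not been taking place". There is no list of expected events and no reference to known effects of the intervention.

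The subsection on SAE reporting then sets the routes:

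- "All SAEs will be reported to the Chief Investigator within 24 hours of awareness of the SAE".
- "All SAEs of a related and unexpected nature will require onward reporting to the main REC". The same related and unexpected class goes to the Sponsor at once. All investigators are also told, and the TSC is told on the Sponsor's timeframe.
- "SAEs which after review are not thought to be treatment related will be brought to the TSC's attention at their next scheduled meeting".
- Counts and particulars of AEs and SAEs go to the Trial Management Group (TMG) and the TSC at regular but unstated intervals.

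Part (a) of the AE definition names the episodes of most concern: "A significant episode during or shortly after treatment (e.g. suicide, suicide attempts, mental health related hospital admissions". It says that these amount to harm or severe harm if treatment caused them or they are related to it.

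**The concern.** Expectedness normally decides which related events need outside eyes quickly. Here it is measured against what might happen to the participant anyway. The trial enrols adults with a PHQ-9 score of 10 or more, so the serious events most relevant to a depression intervention are also ones that the underlying condition can produce. A classification rule built on background anticipation can therefore divert the very harms that the AE definition singles out.

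What is at stake is the speed and independence of review. If guided self-help worsened suicidality in some participants, the events showing it could be judged related, be labelled expected, and reach neither the REC nor, immediately, the Sponsor. The first person obliged to see them is the Chief Investigator, who also assigns the label.

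**Working it through.** No figure in the plan is at issue, so the check sets the rules side by side and follows each type of SAE through them.

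**Step 1. Can the named events be SAEs?** Section 21 counts death and hospitalisation as serious, so a suicide or a mental health admission qualifies directly. A suicide attempt can qualify as life-threatening or medically significant.

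**Step 2. Can they be classed as expected?** The protocol itself foresees suicidality in this population. Section 11 has a suicide-risk exclusion and adds: "Risk may increase during the study as evidenced by session by session administration of the PHQ-9 for those in the GSH group". Nothing in Section 21 prevents the answer yes to the expectedness question for such an event in a depressed participant.

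**Step 3. Can they be related and expected together?** Yes. Causality and expectedness are separate items, and neither is made conditional on the other. Section 21 does not say which causality grades count as related. I take possibly, probably and definitely to count, leaving only unrelated outside.

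**Step 4. Where does each combination go?**

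| SAE class | Chief Investigator | REC | Sponsor | TSC |
|---|---|---|---|---|
| Related, unexpected | 24 hours | Yes | Immediately | On the Sponsor's timeframe |
| Related, expected | 24 hours | No | General reporting only, untimed | General reporting only, untimed |
| Unrelated, unexpected | 24 hours | No | General reporting only, untimed | Next scheduled meeting |
| Unrelated, expected | 24 hours | No | General reporting only, untimed | Next scheduled meeting |

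The general reporting in the table comes from two places: the regular TMG and TSC reports in Section 21, and the Committees section, which gives the TMG the task of reporting AEs and SAEs to the TSC, DMEC, sponsors and funders. Neither sets an interval, and neither reaches the REC.

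**Result.** One of the four classes, related and expected, has no sentence of its own and no deadline after the Chief Investigator. The order is also inverted: an SAE judged unrelated has a firmer TSC deadline than one judged related but expected.

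**The case against.** A reader might infer that such events drop out of onward reporting, or appear only as totals. The documents do not support that:

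- Every SAE reaches the Chief Investigator individually within 24 hours.
- An event that may be related needs a report form within 5 working days.
- The record for related SAEs is event by event: "All SAEs that occur in relation to the intervention must be recorded, together with data including date of onset and resolution, outcome, severity and causality".
- The regular reports carry particulars as well as counts.
- The Committees section extends reporting to the DMEC, sponsors and funders with no exception for expected events, and gives the DMEC a role in reviewing and advising on those reports.

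All of this stands, and it rules out saying that the event has no individual route or would never reach the Sponsor.

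Nor does the protocol say that suicide attempts or admissions are expected. The question can be read case by case, about this event in this participant, and Sections 11 and 12 screen out people whose current suicidality makes a low-intensity intervention unsuitable. On that reading, an event graded probably or definitely related would seldom also be one anticipated without the research, and the overlap would lie mainly with possibly related events. This narrows how often the problem would arise. It does not remove it, because the wording allows the broader reading, and the possibly related grade is where most of the doubtful cases would fall.

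Section 21 also refers to Sponsor procedures that are not shown. As written, they govern how related and unexpected SAEs are handled and do not widen that class.

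**Conclusion.** The point holds as a defect of definition and timing. Followed as written, Section 21 allows a related suicide attempt or mental health admission to be classed as expected. It then misses REC reporting and immediate Sponsor reporting, and only untimed general reporting is left after the first 24 hours. This affects one of the four relatedness-by-expectedness classes, and all three examples in part (a) of the AE definition can fall into it.

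The conclusion rests on two assumptions: that the three causality grades above unrelated count as related, and that the expectedness question may be answered from the background course of depression. The protocol gives no expected event rate, so the number of events affected cannot be estimated. With 70 participants it is likely to be small. The reason to act is that the rule applies to the most serious harms, not that it would apply often. It should be corrected, but it is not evidence that these events would go unseen.

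**What to change.** In Section 21:

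1. State that every SAE judged possibly, probably or definitely related is reported individually and immediately to the Sponsor, the DMEC and the TSC, whatever its expectedness.
2. State that an event is not classed as expected for REC reporting solely because it can occur in the underlying depression.
3. Reconcile the Committees section with the assessment and reporting rules in Section 21, so that each combination of relatedness and expectedness has a named recipient and a timeframe.

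Replacing the question with a list of foreseeable intervention effects would not be enough alone. The AE definition already names suicidal acts and deterioration as potential harms, so such a list might include them and make them expected again. The first change secures prompt Sponsor and committee review under any definition; the second restores access to the REC.

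The cost is a few sentences of protocol text and a few more individual SAE reports in a 70-person trial. Trial design, sample size and data collection are unaffected.
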